Family-centred care (FCC) is, in fact, developmentally supportive care that helps develop bonding (12). Intermittent kangaroo mother, as a part of FCC, benefits from maternal-neonatal bonding (13). Similarly, the role of maternal involvement in pre-feeding sensorimotor stimulation is a hidden corner in research. To our knowledge, not even a single international or national study is available in this regard.

In resource-constrained setups with limited properly trained speech therapists and neonatal nurses, mothers can be involved in pre-feeding sensory motor stimulation after training and teaching to improve their feeding performance. Within this context, the current study aims to determine the following: 1) the maternal role in sensory-motor stimulation for oral feed establishment in preterm neonates, 2) determine the effect of sensory-motor stimulation offered by the mother on the onset of oral feeding, and 3) the efficiency of mother-mediated stimulation techniques on oral feeding compared to trained nurses.

Keywords

Prematurity sensory-motor stimulation oral feed establishment, feeding intervention

Material and methods

An interventional, prospective, randomized control trial was conducted after ethical approval from the Institutional Review Board of Fatima Memorial Hospital (FMH-07-2021-IRB-929-M). The authors confirm that this intervention's ongoing and related trials are registered in the ClinicalTrials.gov platform—accession number NCT05484726. The study protocol can be accessed at <https://www.clinicaltrials.gov/ct2/show/NCT05484726>.

Study hypothesised that preterm babies who receive sensory motor stimulation from their mothers as compared to trained nurses, are

- Start taking oral feed at the same time as compared to the control group
- Take the same amount of milk at the commencement of oral feeding
- Take milk with equal efficiency
- Not face more adverse effects

The study period spans 16 months, from March 2022 to July 2023, in the department of Neonatology, Fatima Memorial Hospital, Lahore. We enrolled all preterm neonates of gestation age 28 to 34 weeks who were admitted to NICU during the study period after seeking consent from parents or guardians. All these neonates were haemodynamically stable, established gavage feed, had no respiratory distress, no need for respiratory support except LFNC and did not receive any kind of analgesics at time of enrollment.

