However, all those neonates having major anomalies incompatible with life, major malformations, syndromic babies, cleft lip and palate, genetic disorders, haemodynamically unstable babies including IVH (grade III & IV), haemodynamically significant PDA (HsPDA) requiring antifailure therapy, NEC (stage II & III) or anemia requiring blood transfusion. All those neonates with adverse events including cough with choking, breath holding, choking, aspiration, tachycardia HR > 200/min, bradycardia HR < 100/min, apnea > 15 sec, tachypnea RR > 70/min while stimulation or feeding were excluded.

Protocol

Interventional Study Model: Factorial Assignment

- Maternal involvement in perioral sensory-motor stimulation be in three stages
 - Observer status
 - Performing under supervision
 - Independent
- Intervention period: 5 days as
 - Training phase (T): T1 and T2 (for mothers by the nurse)
 - Direct feeding phase (D): F1, 2, and 3 (oral feed was offered to neonate)
- Stimulation for 7 minutes and 15 minutes before feeding twice a day at 1100 and 1700 hrs.
- Two groups
 - Intervention group (G I): by mothers
 - Control group (G II): by staff nurses

Number of Arms: 2

Masking: Single (Care Provider)

The mothers, medical staff involved in general care, nursing staff involved in the intervention, and doctors conducting the assessment of oral feeding skills (OFS) were all blinded to allocation. The nursing staff was informed at the time of intervention that participating infants received either sensory motor stimulation or sham oral stimulation depending on group allocation.

Allocation

Randomization was done using a random Alloc Software environment. Gestation age-based stratification was done using 3 blocks design of 28 to 30, 30+1 to 32 & 32+1 to 34. Random allocation of neonates into the intervention or control groups by stratum using lottery method.

Blinding

The mothers, medical staff involved in general care, nursing staff involved in intervention and doctors conducting the assessment of oral feeding skills (OFS) were all blinded to allocation. The nursing staff was informed at the time of intervention that participating infants received either sensory motor stimulation or sham oral stimulation depending on group allocation.

Sample size

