 - Step 1: With the help of the index finger, on the external surface of the cheek, make a circle starting from the angle of the mouth towards the ear then back 7x each cheek
 - Step 2: While holding both sides of the cheek with help of the thumb and index finger repeat step 1 7x each cheek
 - Step 3: Move index finger from one corner to opposite one over both lips separately 7x each lip
 - Step 4: Gentle massage and compress the gums from center to back of mouth 7x each half of the gum
 - Step 5: Move the finger from front to back on the hard palate while applying gentle pressure 7x
 - Step 6: Displace the center of the tongue with gentle pressure 7x
 - Offer pacifier at the end 2 minutes Note: 7x means 7 times

Control group / Sham Comparator (Group II)

All steps were same as intervention group and was performed by trained staff nurses

Data Collection

All relevant maternal and neonatal data (baseline measures) were collected on a specially designed proforma.

Baseline measures

- Maternal demographic and clinical data include
 - Age in years
 - Gravidity / number of pregnancies measured in numbers as primigravida (PG), 2-3 or ≥ 4)
 - Educational qualification as uneducated, primary, secondary or higher
 - Previous preterm baby measured as yes or no
 - Job status as working-lady or home-maker
 - Diabetes mellitus, hypertensive disorders and anemia as yes or no
- Neonatal demographic data includes
 - Gender as male or female
 - Gestation age measured in weeks
 - Mode of delivery as spontaneous vaginal delivery (SVD) or low segment caesarian section (LSCS)
 - Birth weight measured in kg
 - Weight for gestation age. It can be appropriate for gestation age (AGA), small for gestation age (SGA) or large for gestation age (LGA)
 - Place of birth as inborn or out-born
 - Neonates with respiratory failure may need respiratory support that was measured as
 - Requirement of invasive mechanical ventilation (IMV) along with duration in days as median with IQR

- Non invasive ventilation (NIV) along with duration in days as median with IQR
- Oxygen as low flow nasal cannula (LFNC) along with duration in days as median with IQR
- Neonates with prophylactic caffeine therapy given to all neonates < 32 weeks of gestation age
- Respiratory distress syndrome (RDS) was diagnosed on clinical and radiological features of reticulo-nodular shadowing
- Apnea was diagnosed on basis of breath holding spells for > 20 second

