- Hemodynamically significant patent ductus arteriosus (HsPDA) diagnosed by echocardiography
- Necrotizing enterocolitis (NEC) diagnosed using modified Bell's scoring (stage 1)
- Feeding intolerance diagnosed as aspirates > 20% of previous feed ± abdominal distension of > 2cm from base line
- Sepsis (leukocytosis or leukopenia or ANC<150 along with raised CRP and platelets <100 and or positive blood culture)
- Seizures
- Discharge weight in kg
- Duration of stay in NICU in days
- Neonatal feeding characteristics at time of enrollment in study include
 - Postmenstrual age (PMA) measured in weeks
 - Chronological age (ChA) measured in weeks
 - Time/duration to achieve full gavage/tube feed measured in days
 - Daily milk intake (ml/kg/day) when sensory motor stimulation was started
 - Volume of feed prescribed for each feed (ml)

The **outcome** measured were documented daily twice a day (11.00 and 17.00 hrs) until achievement of full oral feed. Full oral feed was volume of 120-140ml/kg/day taken orally. However, to make calculations concise, for both groups, all outcome parameters were documented on proforma for fixed time (11.00 am) for D1, D2, D3, D5, D7 and D14.

- Primary Outcome Measure
 - Transition time to full oral feeding is the time interval between commencement of perioral sensory stimulation on D1 to establishment of full oral feed in both groups. It was done daily till 14th day of perioral sensory motor stimulation. Transition time to full oral feeding was the day at which baby was able to take oral feed of volume of 120-140ml/kg/day.
 - Improvement (change) in efficiency oral feed establishment in terms of amount and time. It was classified into four levels depending upon the level of maturity in ascending order as follows:
 - Level 1: PRO < 30% and RT < 1.5 ml/min
 - Level 2: PRO < 30% and RT ≥ 1.5 ml/min
 - Level 3: PRO ≥ 30% and RT < 1.5 ml/min
 - Level 4: PRO ≥ 30% and RT ≥ 1.5 ml/min

For our RCT, efficacy was measured as the achievement of L4 for the intervention group vs the control group.

- Adverse outcome monitoring was done for every neonate from first day of enrollment in study (D1) till establishment of full oral feed (by D14 expected). These include non-life threatening adverse events including cough, tachycardia HR 180-200/min, bradycardia HR120 - 100/min, , tachypnea RR 60 - 70/min while maintaining SpO2 of >90% at room air
- Secondary Outcome Measure:
 - Total volume (TV) taken during each feed

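### The adverse-event outcome carries a saturation and room-air condition that the exclusion list does not complement, so desaturation and some mild events in infants with low saturation or on oxygen have no stated place.

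*Combined protocol and SAP*

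**What the plan says.** The combined document handles events during stimulation or feeding in two places.

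- **Outcome** (Data Collection, Primary Outcome Measure). Monitoring runs from D1 until full oral feeding. The events are introduced as "These include non-life threatening adverse events including cough, tachycardia HR 180-200/min, bradycardia HR120 - 100/min", and the sentence closes with "tachypnea RR 60 - 70/min while maintaining SpO2 of >90% at room air".
- **Exclusion** (Material and methods, exclusion paragraph). Infants are excluded for "adverse events including cough with choking, breath holding, choking, aspiration, tachycardia HR > 200/min" and for "bradycardia HR < 100/min, apnea > 15 sec, tachypnea RR > 70/min while stimulation or feeding were excluded". This list sets no saturation threshold and no condition on oxygen.

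Two other places bear on the room-air condition. Eligibility requires "no need for respiratory support except LFNC", so an infant on LFNC may enter. Baseline measures record LFNC as oxygen: "Oxygen as low flow nasal cannula (LFNC) along with duration in days".

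The fourth hypothesis is that infants stimulated by their mothers do not have more adverse effects than those stimulated by nurses. Table 3 gives the number of infants with an adverse event by day, and Results reports no significant difference.

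**The concern.** Mild events belong to the outcome and severe events to the exclusion list, so together the two lists should place every relevant event. They do not. The outcome has a saturation and room-air condition with no counterpart in the exclusion list, so an event can fail the first and not meet the second.

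The omission runs in an awkward direction. Mild tachypnea with saturation held above 90% in room air is counted, while the same tachypnea with a fall to 90% or below is not. If one arm had more desaturation with otherwise mild events, its tabulated rate could look lower for that reason. The room-air condition also does not fit the eligibility rule: an infant who is properly enrolled on LFNC cannot satisfy it, yet stays in the denominator of 49 or 48.

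This bears on an outcome listed as primary and on the only hypothesis that concerns safety.

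**Working it through.** **1. Where each kind of event falls.** The closing phrase can be read in two ways, so both are shown.

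| Event during a session | Outcome, if the phrase governs the whole list | Outcome, if it governs tachypnea only | Exclusion list |
|---|---|---|---|
| Desaturation alone | not named | not named | not named |
| Cough, HR 180-200 or HR 100-120, with SpO2 90% or below | not counted | counted | not named |
| The same events on LFNC, SpO2 above 90% | not counted | counted | not named |
| RR 60-70, with SpO2 90% or below or on LFNC | not counted | not counted | not named |
| Severe event (for example HR above 200, HR below 100, RR above 70, aspiration), any saturation or support | not in outcome | not in outcome | named |

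The first and fourth rows are gaps under both readings. The second and third are gaps only under the first reading. The last row is no gap, because the exclusion list has no saturation or oxygen condition; a desaturation that accompanies a severe event is covered through that event.

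**2. How many infants could be affected through the room-air condition.** Table 1 gives 47 of 49 and 43 of 48 infants ever on LFNC: 47 + 43 = 90, and 90/97 = 92.8% (95.9% v 89.6%). This counts use at any time. The number on LFNC at enrolment or at a session is not given, so 90 is an upper limit and the true number may be far smaller.

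**3. The tabulated result that rests on the definition.** Table 3 gives 36/49 (73.5%) v 31/48 (64.6%) on D1, with p = 0.234. A one-sided Fisher exact test on these counts gives 0.2337, which reproduces it. The two-sided Fisher value is 0.385. The sidedness is a separate matter; the two-sided value is used below.

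**4. How sensitive that result is.** Table 3 counts infants, so an omitted event changes D1 only if it occurred in an infant not already counted. At most 49 - 36 = 13 and 48 - 31 = 17 infants could be added. The additions below are assumptions that show the range, not estimates.

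| Infants added on D1 (mothers, nurses) | Rates | Difference | Two-sided Fisher p |
|---|---|---|---|
| 0, 0 | 73.5% v 64.6% | 8.9 points | 0.385 |
| 5, 0 | 83.7% v 64.6% | 19.1 points | 0.038 |
| 5, 5 | 83.7% v 75.0% | 8.7 points | 0.325 |
| 0, 6 | 73.5% v 77.1% | -3.6 points | 0.815 |
| 13, 0 | 100% v 64.6% | 35.4 points | <0.001 |
| 0, 17 | 73.5% v 100% | -26.5 points | <0.001 |

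A balanced omission leaves the comparison about where it is. Five omitted infants, all in the mothers' arm, would change it. The documents give nothing with which to choose between these rows.

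**The case against.** Four points on the other side have force.

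- **Severe events on oxygen.** A reader might infer that no event in an infant on oxygen has a place anywhere. That is not so, as the last row of the first table shows. This stands and limits the point to mild events and isolated desaturation.
- **Reach of the closing phrase.** The phrase follows the last item and may qualify tachypnea alone. Cough or a mildly abnormal heart rate with low saturation would then be counted. This stands as a possible reading. It narrows the gap but does not close it, and two assessors could classify the same event differently.
- **Open lists.** Both lists are introduced as examples, so a reader should not infer that desaturation went unrecorded; the documents do not show that. But an open list does not cancel an explicit condition inside it, and an event named nowhere is counted only at the assessor's discretion.
- **No evidence of imbalance.** Nothing shows that omitted events differed between arms. This also stands: the shift between arms is a possibility, not a finding.

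A reader might also want to add the wording on breathing pauses. It does not support this point. Breath holding is on the exclusion list, so it is not an event without a place, and the definition in Baseline measures ("Apnea was diagnosed on basis of breath holding spells for > 20 second") is a baseline diagnosis that need not match a session event. What remains is that breath holding of unstated length and apnea above 15 seconds overlap within the exclusion list, which has nothing to do with saturation.

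Nor do the documents show that D1 is the day most affected. With 67 of 97 infants already counted, 30 could be added on D1, against 97 - 28 = 69 on D2.

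**Conclusion.** The concern holds in a limited form. Isolated desaturation is named in neither list, and mild tachypnea with low saturation or on LFNC is outside both under either reading of the sentence. The remaining mild events with low saturation or on LFNC are outside both only if the phrase governs the whole list.

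This is more than missing detail: a stated condition for counting can drop the worse form of a mild event from a primary outcome, and it conflicts with the eligibility of infants on LFNC. The number of events lost cannot be derived. The tabulated D1 comparison would withstand a balanced omission, but not one of five infants confined to the mothers' arm. The finding of no difference in adverse events is therefore secure only for the events that the definition admits.

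**What to change.** Enrolment is over and results are tabulated, so the remedy lies in clarification, re-tabulation and the wording of the conclusion.

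1. State what the saturation and room-air phrase governs, whether saturation and LFNC status were recorded at sessions, and how infants on LFNC were classified.
2. Drop the phrase as a condition for counting. Count the listed mild events whatever the saturation or oxygen support. Report desaturation during sessions as a separate category by arm, with LFNC status.
3. If the data exist, re-tabulate the adverse-event rows of Table 3 on this basis and label the result post hoc, beside the present rows.
4. If they do not, state that desaturation was not assessed and limit the conclusion to mild events without desaturation in room air, or to whatever the clarified phrase covers.
5. Separately, reconcile the overlapping breath-holding and apnea items in the exclusion list.

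The cost is one re-tabulation, or a sentence or two of limitation. Applying the present definition already required saturation to be read, though whether it was kept is not stated. The downside is that reported adverse-event rates may rise and the re-tabulated comparison is not prespecified.

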 - Volume taken during the first 5 min (TV₅) out of total feed taken orally
 - Rate of transfer (RT) ml/min i.e., how long it neonate takes to finish oral feed.
 - Overall transfer (OT percent) volume taken/total volume prescribed. It shows trend towards oral feed establishment.
 - Proficiency (PRO percent) volume taken during the first 5 min/total volume prescribed.
 - SSB (Suck Swallow Breaths) coordination coordinated, developed pattern of suck swallow and breathe. It is a subjective assessment.

Statistical analysis

The statistical software IBM SPSS Statistics version 21 (SPSS, Chicago, IL) was used for the statistical analysis of the data. Appropriate bivariate analysis was performed to identify the unadjusted differences between the cases and controls. Categorical variables were expressed as frequencies and percentages. According to Shapiro Wilk test all continuous variables were asymmetrically distributed. Mann–Whitney U test was used for nonparametric continuous variables and were described as medians and inter quartile range (IQR). Fisher exact/Chi square test was used to compare categorical variables. Mann-Whitney test was used to compare continuous variables. The p-value of < 0.05 was taken as statistically significant.

Results

During the research period, 1009 newborns were admitted to the Neonatal Intensive Care Unit (NICU). Among them, 142 were born prematurely, with gestational ages falling between 28 and 34 weeks. Out of the preterm neonates, a total of 130 were eligible for the study, as 12 had to be excluded for various reasons. These exclusions included 2 cases where mothers experienced serious postnatal complications, 1 instance of parental refusal to participate, 1 case with incomplete data, and 8 cases that did not meet the inclusion criteria due to different reasons such as syndromic features, cleft lip and palate, suspected inborn error of metabolism (IEM), intraventricular hemorrhage (grade IV), and hemodynamically significant patent ductus arteriosus (HsPDA). Consequently, 130 neonates were included in the study and randomly assigned, with 65 in each group for intervention and control. Sensory motor stimulation (SMS) was administered to 107 of these neonates, and the study was completed with 97 neonates (as illustrated in Figure 1).

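### Outcomes recorded on up to six days in the same infant are compared only day by day (42 of the 43 p-values in Table 3), with no summary over days, no arm-by-day test and no difference with a confidence interval for any outcome

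*Combined protocol and SAP*

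**What the plan says.** Under the outcome definitions, recording is "documented daily twice a day (11.00 and 17.00 hrs) until achievement of full oral feed", but for the analysis "all outcome parameters were documented on proforma for fixed time (11.00 am) for D1, D2, D3, D5, D7 and D14". The first-listed primary outcome has a single value per infant: "Transition time to full oral feeding was the day at which baby was able to take oral feed of volume of 120-140ml/kg/day". The second is change in the efficiency of oral feeding, measured as reaching level 4 (L4). Volume per feed (TV), volume in the first 5 minutes (TV5), rate of transfer (RT), overall transfer (OT), proficiency (PRO) and suck-swallow-breathe coordination (SSB) are secondary.

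The Statistical analysis section describes the approach as follows: "Appropriate bivariate analysis was performed to identify the unadjusted differences between the cases and controls". For categorical data, "Fisher exact/Chi square test was used to compare categorical variables". For the rest, "Mann-Whitney test was used to compare continuous variables. The p-value of < 0.05 was taken as statistically significant". It names no repeated-measures method, summary measure over days, effect estimate or confidence interval. The Results section then concludes that feeding skills in the two arms are comparable.

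**The concern.** Change over time is a primary outcome, and the document describes OT as showing a trend towards oral feeding. Both are statements about a course, but every L4 and OT test is a snapshot of one day. The hypotheses are of sameness, so the reader needs to know how large a mother-versus-nurse difference the data still allow. Separate non-significant daily tests do not say. A small, steady difference in one direction could leave every daily test non-significant, and nothing in the analysis would collect that evidence.

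**Working it through.** The document states no count of tests and no precision target, so the check starts from Table 3.

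**1. Count of p-values (NA cells excluded).**
- Time to full oral feed: 1
- Adverse events: 4 (D1, D2, D3, D5)
- L4: 3 (D5, D7, D14)
- TV, TV5, RT, OT, PRO: 5 × 6 = 30
- SSB: 5 (D14 is NA)

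The total is 1 + 4 + 3 + 30 + 5 = 43, of which 43 - 1 = 42 are day by day. The smallest is 0.180 (SSB, D2).

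**2. False positives.** Under no difference, 43 × 0.05 = 2.15 tests would be expected below 0.05. The chance of at least one is 1 - 0.95^43 = 0.89 if the tests were independent. With an assumed common correlation of 0.3 / 0.5 / 0.7 among all 43 tests, simulation gives about 0.76 / 0.59 / 0.39. In the event none is below 0.05.

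**3. What a single day can say.** These are approximate intervals from the Table 3 counts, with SE = √[p₁(1-p₁)/49 + p₂(1-p₂)/48]:
- L4 at D14: 35/49 - 36/48 = 0.714 - 0.750 = -0.036; SE 0.090; 95% CI -21 to +14 points.
- Adverse events at D1: 36/49 - 31/48 = 0.735 - 0.646 = +0.089; SE 0.094; 95% CI -9 to +27 points.
- SSB at D2: 33/49 - 27/48 = 0.673 - 0.563 = +0.111; SE 0.098; 95% CI -8 to +30 points.

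**4. Patterns the daily tests cannot assess.** SSB is numerically higher in the mother arm on all five tested days (46.9 v 45.8%, 67.3 v 56.3%, 67.3 v 66.7%, 81.6 v 77.1%, 79.6 v 75.0%). Median volume per feed is equal on D1, higher in the mother arm on D2 to D7 (5 v 3, 7 v 4, 8 v 6.5, 9 v 7.5 ml) and slightly lower on D14 (15 v 15.5 ml). Neither pattern is claimed to be real.

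**5. Precision of an average over six days.** If each day has the same variance and any two days have correlation ρ (assumed), the variance of the six-day mean relative to one day is (1 + 5ρ)/6. For ρ = 0.3 / 0.5 / 0.7 this is 0.417 / 0.583 / 0.750. The SE ratio is then 0.645 / 0.764 / 0.866, which is 35% / 24% / 13% smaller.

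Table 3 does not support equal variance on the raw scale. OT interquartile widths over D1 to D14 are:
- mother arm: 21, 29, 34.5, 32, 27.5, 13 (sum 157; sum of squares 4421.5)
- nurse arm: 20.7, 21, 29, 32, 54, 12.1 (sum 168.8; sum of squares 5796.9)

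Take width as a stand-in for SD; the scale factor cancels in the ratio. The variance of the six-day mean in one arm is [(1-ρ) × sum of squares + ρ × sum²]/36. At ρ = 0.3 that is (0.7 × 4421.5 + 0.3 × 157²)/36 = 291.4 and (0.7 × 5796.9 + 0.3 × 168.8²)/36 = 350.2. The arm difference then has variance 291.4/49 + 350.2/48 = 13.24, against 13²/49 + 12.1²/48 = 6.50 for D14 alone. The SE ratio is √(13.24/6.50) = 1.43. The same steps at ρ = 0.5 and 0.7 give 1.67 and 1.88. The raw six-day mean of OT is therefore 43% / 67% / 88% less precise than D14 alone.

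**The case against.** Four points on the other side stand.

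- A reader might infer that every outcome is split over six days. Time to full oral feed is not: it has one value and one comparison, 10 (7–13) against 9 (7–13) days, p = 0.531. All it lacks is a difference with an interval.
- A reader might infer that the conclusion rests on inflated false positives. It cannot, because no p-value is below 0.05 and a spurious significant day would count against the claim of sameness.
- A reader might infer that the tests are invalid because they ignore the correlation between days. Each daily test uses one value per infant, so it is sound as a test of that day. What is lost is a summary and, on a suitable scale, precision.
- Day-specific comparison has a purpose. One hypothesis concerns the amount taken when oral feeding starts, and delivery in the intervention arm changes from D1 to D3 as the mother takes over. An equal average mixes those stages.

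The number of values per infant is also uncertain. Recording was to run until full oral feed, whose lower quartile is 7 days, and Table 3 gives no n by day. SSB at D14 is reported for all 49 and 48 infants, however, so recording does not seem simply to have stopped.

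None of this supplies the missing summary over days, arm-by-day test or interval.

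**Conclusion.** The concern holds in limited form. For the outcomes behind 42 of the 43 p-values, the analysis never combines the days and never tests whether the arm difference changes between them. No outcome, including time to full oral feed, has an estimated difference with a confidence interval. This matters because change is a primary outcome and comparability is concluded from non-significance, while single-day intervals for the binary outcomes in step 3 span about 35 to 38 points.

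The gain in precision is conditional. A standard error 35 / 24 / 13% smaller needs a common scale within each day and an assumed equal correlation of 0.3 / 0.5 / 0.7. The documents do not support a gain over every single-day test on the raw scale, as OT at D14 shows. The actual estimates need infant-level data. This is a cheap and worthwhile improvement; it does not show that the reported results are wrong.

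**What to change.** Add to the Statistical analysis section, labelled post hoc:

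- **TV, TV5, RT, OT, PRO:** one mixed model, or GEE with robust errors, per outcome, on values ranked or standardised within day. Include arm, day as categories, arm-by-day and gestational-age band (the randomisation stratum), with infant as the repeated unit.
- **SSB, L4 and adverse events:** logistic GEE with the same terms, restricted to days that carry information: SSB on D1 to D7 (all infants are coordinated on D14), L4 on D5, D7 and D14, adverse events on D1, D2, D3 and D5. Adverse events on D5 are 2 against 0, so that day's arm-by-day term needs merging with D3 or a penalised fit.
- **Report per outcome:** one averaged arm difference with 95% CI and the arm-by-day test. Keep a D1 contrast with CI for the hypothesis about intake at the start of oral feeding. Show the other daily values without p-values, and give n by day.
- **Time to full oral feed:** a difference in days with 95% CI, for example Hodges–Lehmann, beside the existing test.

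The cost is SAP wording and one model per outcome on data already held; no new measurement is needed. The downsides are model assumptions for skewed or incomplete daily data, a ranked or standardised difference that is harder to read than millilitres, and an average that mixes stages of delivery. The arm-by-day test and the D1 contrast partly offset the last.
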